5.1.2 AE date imputation

5.1.2.1 Adverse Event End Date Imputation

- 1. If the AE end date month is missing, the imputed end date should be set to the earliest of the (treatment follow up period date, 31DECYYYY, date of death).
- 2. If the AE end date day is missing, the imputed end date should be set to the earliest of the (treatment follow up period date, last day of the month, date of death).
- 3. If AE year is missing or AE is ongoing, the end date will not be imputed.

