2.1.1 General definitions

- The study treatment is sacubitril/valsartan.
- The date of first administration of study treatment during this study is the day of the first non-zero dose of sacubitril/valsartan after patient is enrolled in CLCZ696B2319E2 study.
- The date of last administration of study treatment is the day of the last non-zero dose of sacubitril/valsartan.
- The study period starts with the date of the signature on informed consent (Visit Day 1, the same day as Visit 599 (EOS visit) of PANORAMA-HF OLE study) and ends with the date of end-of-study or premature study discontinuation visit (Visit EOS).
- The treatment period starts with the date of first administration of study treatment in CLCZ696B2319E2 study and ends with the date of treatment disposition. In the case that no EOS visit is undertaken (e.g., because the participant died or withdrew from the study without such a visit), the treatment period ends with the death/withdrawal date, or the last dose taken.
- Baseline is defined as the variable on the date of Visit Day 1 regardless of whether the study treatment is administered on Visit Day 1.
- Study day is defined as actual date date of Visit Day1 + 1

- Treatment day is defined as actual date the date of first administration of study treatment + 1
- Each scheduled visit date is defined using the study day as follows:
 - Visit M3 = day 91
 - Visit M6 = day 183

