2.7 Safety analyses

2.7.1 Adverse events (AEs)

All AEs will be identified using Medical Dictionary for Regulatory Activities (MedDRA). The MedDRA version used for reporting the study will be described in a footnote.

An AE with its severity increased should be considered and recorded as a new AE.

The following adverse events will be summarized by primary system organ class, and preferred term as appropriate using numbers and percentages of patients with at least one adverse event in the corresponding class. Similarly, Summarization by maximum severity will be conducted.

- Any serious adverse event (treatment emergent or not)
- Treatment emergent adverse event (TEAE)
- Treatment emergent serious adverse event

TEAEs are defined as any recorded AE with its start date (recorded or imputed) on or after Visit Day 1 (the date of first administration of study treatment if treatment did not start at Visit Day 1) and end date as the end date of the treatment period or the date of last dose taken as reported in the DAR page. Any AE happening after treatment discontinuation but still within the study period (e.g., where patient did not discontinue the study on the same date of treatment discontinuation) would not be considered as a TEAE and will be reported in the listing of AE.

All outputs will be created for AEs regardless of study-drug relationship, and for study-drug related AEs. Study drug related AEs are defined as any recorded AE with "Relationship to study treatment" answered as "Related". Serious adverse events (SAEs) are defined as any recorded AE with "Was the adverse event serious?" answered as "Yes".

The following rules are applicable to the summaries:

- If a patient reported more than one AE with the same PT, the patient will be counted only once with the greatest severity at the PT level
- If a patient reported more than one AE within the same SOC, the patient will be counted only once with the greatest severity at the SOC level, where applicable.

In addition, the following information will be listed for all AEs.

- Subject ID
- Date of Study Treatment start
- Start date (Treatment day)

Displays the start date entered on CRF or imputed and corresponding Treatment day (the number of days from the date of treatment start).

• End date (Treatment day)

Displays the end date entered on CRF or imputed and corresponding Treatment day (the number of days from the date of treatment start).

Duration

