 - c. Else if the AE month is equal to the treatment start date month or greater than the treatment start date month, the imputed AE start date is set to the later of (month start point (01MONYYYY), AE start reference date + 1 day).

If complete (imputed) AE end date is available and the imputed AE start date is greater than the (imputed) AE end date, then imputed AE start date should be set to the (imputed) AE end date.

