5.1.3 Concomitant medication date imputation

- ← Concomitant medication end date imputation
- 1. If CM end day is missing and CM month/year are non-missing then impute CM day as the minimum of treatment end date and the last day of the month.
- 2. If CM end day/month are missing and CM year is non-missing then impute CM day as the minimum of treatment end date and the end of the year (31DECYYYY).
- 3. If CM day/month/year is missing then use the treatment end date + 1 day as the imputed CM end date.

- 4. If imputed CM end date is less than the CM start date, use the CM start date as the imputed CM end date.
- ← Concomitant medication start date imputation

The following table explains the notation used in the logic matrix. Please note that missing start dates will not be imputed.

	Day	Month	Year
Partial CMD Start Date	Not used	MON	YYYY
Treatment Start Date	Not used	TRTM	TRTY

The following matrix explains the logic behind the imputation.

	MON MISSING	MON < TRTM	MON = TRTM	MON > TRTM
YYYY	(1)	(1)	(1)	(1)
Missing	Uncertain	Uncertain	Uncertain	Uncertain
YYYY < TRTY	(2.a)	(2.b)	(2.b)	(2.b)
	Before Treatment Start	Before Treatment Start	Before Treatment Start	Before Treatment Start
YYYY = TRTY	(4.a)	(4.b)	(4.a)	(4.c)
	Uncertain	Before Treatment Start	Uncertain	After Treatment Start
YYYY > TRTY	(3.a) After Treatment Start	(3.b) After Treatment Start	(3.b) After Treatment Start	(3.b) After Treatment Start

- 1. If the CM start date year value is missing, the imputed CM start date is set to one day prior to treatment start date.
- 2. If the CM start date year value is less than the treatment start date year value, the CM started before treatment. Therefore:
 - a. If the CM month is missing, the imputed CM start date is set to the mid-year point (01JulYYYY).
 - b. Else if the CM month is not missing, the imputed CM start date is set to the midmonth point (15MONYYYY).
- 3. If the CM start date year value is greater than the treatment start date year value, the CM started after treatment. Therefore:
 - a. If the CM month is missing, the imputed CM start date is set to the year start point (01JanYYYY).
 - b. Else if the CM month is not missing, the imputed CM start date is set to the month start point (01MONYYYY).
- 4. If the CM start date year value is equal to the treatment start date year value:

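### Partial AE end dates are capped at an undefined date with no floor at the AE start, so a late AE can be listed as ending before it began

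*SAP*

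**What the plan says.** SAP 5.1.2.1 has two rules for partial AE end dates. Where the day was not recorded: "the imputed end date should be set to the earliest of the (treatment follow up period date, last day of the month, date of death"). With the month missing, "the imputed end date should be set to the earliest of the (treatment follow up period date, 31DECYYYY, date of death"). The first date in each list appears nowhere else in the SAP. SAP 2.1.1 defines the study period, the treatment period (which "ends with the date of treatment disposition") and the last administration, but no follow-up period. The assessment schedule (Protocol Table 1-2) shows a single treatment period.

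The only AE rule that reconciles start and end closes SAP 5.1.2.2. If an imputed start is later than the end, "then imputed AE start date should be set to the (imputed) AE end date". It acts on imputed starts only and never corrects the end. For medications, SAP 5.1.3 (end-date item 4) corrects the end: "If imputed CM end date is less than the CM start date, use the CM start date as the imputed CM end date".

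SAP 2.7.1 lists AE duration as end minus start plus one day. It sets the TEAE window from the start date: "TEAEs are defined as any recorded AE with its start date (recorded or imputed) on or after Visit Day 1" (or the first dose, if later), with "end date as the end date of the treatment period or the date of last dose taken as reported in the DAR page".

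**The concern.** AEs that start after treatment has stopped are expected. Protocol 8.6.1 continues AE monitoring for at least 30 days after the last dose, and Protocol 8.6.3 takes SAE reporting to 30 days after the last visit. A participant can be off drug for up to 3 consecutive months before being discontinued (Protocol 6.4.1, 7.1). SAP 2.7.1 provides for such events: "Any AE happening after treatment discontinuation but still within the study period" is to be listed and not counted as a TEAE.

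A cap tied to treatment can fall before these events begin. The rule then produces one of two faults, depending on what the site recorded:

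- **Complete start, partial end.** The end is imputed before the recorded start and the listed duration is zero or negative. The start is kept, so TEAE status does not change.
- **Start and end both partial.** The SAP 5.1.2.2 reset pulls the start back to the cap, possibly into a month the site did not record. TEAE status uses the imputed start, so it could change.

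At stake are the dates and durations in the AE listing and, under one reading of the cap, the TEAE and special-interest tables.

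**Working it through.** The plan gives no figure to reproduce. The check applies its rules to assumed dates.

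**General form.** Suppose an AE starts k days after the cap (k ≥ 1), its end date is partial, and the cap is the earliest of the three dates. Then:

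duration = cap − (cap + k) + 1 = 1 − k

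This is 0 for k = 1 and negative for k ≥ 2.

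**Example 1: treatment stopped.** Assumed: first dose 10 Jan 2024, last dose and treatment end 20 Jun 2024, Visit EOS 25 Jul 2024. The end is recorded only as July 2024. The start is 5 Jul, 22 Jul, or only July 2024. For the July-only start, SAP 5.1.2.2 rule 4c gives the later of 1 Jul and 11 Jan, which is 1 Jul, before the reset.

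| Reading of the cap | Cap date | Duration, start 5 Jul | Duration, start 22 Jul | Start imputed when only July is known | TEAE (last column's case) |
|---|---|---|---|---|---|
| Last dose / treatment end | 20 Jun | 1 − 15 = −14 | 1 − 32 = −31 | 20 Jun | Yes |
| Last dose + 30 days | 20 Jul | 16 | 1 − 2 = −1 | 1 Jul | No |
| Visit EOS | 25 Jul | 21 | 4 | 1 Jul | No |
| Visit EOS + 30 days | 24 Aug | 27 | 10 | 1 Jul | No |

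If the end month is also missing, the 22 Jul start gives −31, −1, 4 and 34 days in the same order. Caps at EOS or later cause no fault here, but an AE starting after such a cap would still fail.

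**Example 2: an interruption that is never resumed.** Assumed: first dose 15 Dec 2023, last dose 10 Jan 2024, AE in March 2024, within 3 months of the last dose.

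- Complete start 5 Mar, end recorded as March. Cap 10 Jan: k = 55, duration −54. Cap 9 Feb (last dose + 30): k = 25, duration −24.
- Start and end both recorded as March. Rule 3b gives the later of 1 Mar 2024 and 16 Dec 2023, which is 1 Mar. The reset moves it to 10 Jan or 9 Feb. The recorded month is lost under either cap.

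TEAE status in Example 2 depends on which end of the SAP 2.7.1 window is used. If the treatment period runs to a later treatment disposition, a March AE may already be a TEAE, and only its date changes. If the window ends at last dose, moving the start to 10 Jan makes it a TEAE; moving it to 9 Feb does not.

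**Weight of one patient.** 1/8 = 12.5 percentage points, at the maximum enrolment in SAP Section 3 and with all 8 treated.

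**Example 1 after the fix.** With the cap at the later of Visit EOS (25 Jul) and last dose + 30 days (20 Jul), durations are 21 and 4 days and the July-only AE stays at 1 Jul, not a TEAE. With the floor alone, each failing complete-start case becomes 1 day.

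**The case against.** The strongest reply is that the cap is unlikely to mean last dose or treatment end. Its name refers to follow-up, SAP 2.1.1 has separate terms for last administration and treatment period, and SAP 5.1.3 names the treatment end date when it means that. Monitoring for 30 days after the last dose (Protocol 8.6.1) is a natural candidate. This stands, and on that reading no AE in the examples changes TEAE status. It does not remove the impossible dates: the 22 Jul start still gives −1 day, and the March AE still gives −24 days or loses its month.

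SAP 2.5.4 and 5.1 cite a company standard for date imputation, which may define the term. The standard is not in the documents, and SAP 2.5.4 refers to Section 5.1 for the details, where no definition is given.

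Duration is only a listing column, discrepant data are queried before lock (Protocol 10.1.5.2), and with at most 8 participants an odd value would be seen. That limits the harm. However, a query on the site's data does not repair an imputation rule, and a start moved to the cap gives a 1-day duration that does not look wrong.

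A reader might infer that the primary result is distorted, because AEs are the primary endpoint. The documents do not support this: SAP 2.5.1 and 2.5.2 summarise all AEs, treatment-emergent or not. Nor would post-treatment AEs be reclassified in general, since a complete start never changes TEAE status.

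**Conclusion.** The point holds as a minor defect in the SAP. The cap is undefined, and the AE rules lack the floor that the medication rules have. An AE with a partial end date that starts after the cap gets an end before its start, with duration 1 − k days. If the start is also partial and its recorded month lies wholly after the cap, the start is moved out of that month.

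A change to treatment-emergent status needs two things together: a partial start, and a cap read as last dose or treatment end. The exposure is then the TEAE and special-interest tables, at 12.5 percentage points per patient if all 8 are treated. The primary all-AE summary does not change.

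The dates in the examples are assumptions chosen to show the mechanism. The documents give no frequency for partial AE dates after treatment, and the case should be rare.

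**What to change.** Three changes to SAP 5.1.2:

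1. Define the cap as one date that covers the whole AE collection period, for example the later of Visit EOS and last dose + 30 days, or the last AE assessment if that is later still.
2. Add to 5.1.2.1: if the imputed AE end date is earlier than a complete recorded AE start date, use the AE start date as the imputed end date.
3. Where the start is partial but its month is known, do not let the imputed end fall before the first day of that month. Set it instead to the start date imputed under 5.1.2.2 before the reset, so the reset cannot move the start out of its recorded month.

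The second and third changes are still needed once the cap is defined, as protection for any AE recorded after it. The cost is two or three sentences and minor programming. The document history shows that the SAP was already revised before database lock for clarifications of similar size.

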5.1.2.2 Adverse Event Start Date Imputation

The following table explains the notation used in the logic matrix. Please note that missing start dates will not be imputed.

	Day	Month	Year
Partial Adverse Event Start Date	Not used	MON	YYYY
Treatment Start Date	Not used	TRTM	TRTY

The following matrix explains the logic behind the imputation.

	MON M i ss i ng	MON < TRTM	MON = TRTM	MON > TRTM
YYYY	(1)	(1)	(1)	(1)
Missing	No convention	No convention	No convention	No convention
YYYY < TRTY	(2.a)	(2.b)	(2.b)	(2.b)
	Before Treatment	Before Treatment	Before Treatment	Before Treatment
	Start	Start	Start	Start
YYYY = TRTY	(4.a) Uncertain	(4.b) Before Treatment Start	(4.c) Uncertain	(4.c) After Treatment Start
YYYY > TRTY	(3.a)	(3,b)	(3,b)	(3.b)
	After Treatment Start	After Treatment Start	After Treatment Start	After Treatment Start

Before imputing AE start date, find the AE start reference date.

- 1. If the (imputed) AE end date is complete and the (imputed) AE end date < treatment start date then AE start reference date = min(informed consent date, earliest visit date).
- 2. Else AE start reference date = treatment start date

Impute AE start date;

- 1. If the AE start date year value is missing, the date uncertainty is too high to impute a rational date. Therefore, if the AE year value is missing, the imputed AE start date is set to NULL.
- 2. If the AE start date year value is less than the treatment start date year value, the AE started before treatment. Therefore:
 - a. If AE month is missing, the imputed AE start date is set to the mid-year point (01JulYYYY).
 - b. Else if AE month is not missing, the imputed AE start date is set to the midmonth point (15MONYYYY).
- 3. If the AE start date year value is greater than the treatment start date year value, the AE started after treatment. Therefore:
 - a. If the AE month is missing, the imputed AE start date is set to the year start point (01JanYYYY).
 - b. Else if the AE month is not missing, the imputed AE start date is set to the later of (month start point (01MONYYYY), AE start reference date + 1 day).
- 4. If the AE start date year value is equal to the treatment start date year value:
 - a. And the AE month is missing the imputed AE start date is set to the AE reference start date + 1 day.
 - b. Else if the AE month is less than the treatment start month, the imputed AE start date is set to the mid-month point (15MONYYYY).
 - c. Else if the AE month is equal to the treatment start date month or greater than the treatment start date month, the imputed AE start date is set to the later of (month start point (01MONYYYY), AE start reference date + 1 day).

If complete (imputed) AE end date is available and the imputed AE start date is greater than the (imputed) AE end date, then imputed AE start date should be set to the (imputed) AE end date.

5.1.3 Concomitant medication date imputation

- ← Concomitant medication end date imputation
- 1. If CM end day is missing and CM month/year are non-missing then impute CM day as the minimum of treatment end date and the last day of the month.
- 2. If CM end day/month are missing and CM year is non-missing then impute CM day as the minimum of treatment end date and the end of the year (31DECYYYY).
- 3. If CM day/month/year is missing then use the treatment end date + 1 day as the imputed CM end date.

- 4. If imputed CM end date is less than the CM start date, use the CM start date as the imputed CM end date.
- ← Concomitant medication start date imputation

The following table explains the notation used in the logic matrix. Please note that missing start dates will not be imputed.

	Day	Month	Year
Partial CMD Start Date	Not used	MON	YYYY
Treatment Start Date	Not used	TRTM	TRTY

The following matrix explains the logic behind the imputation.

	MON MISSING	MON < TRTM	MON = TRTM	MON > TRTM
YYYY	(1)	(1)	(1)	(1)
Missing	Uncertain	Uncertain	Uncertain	Uncertain
YYYY < TRTY	(2.a)	(2.b)	(2.b)	(2.b)
	Before Treatment Start	Before Treatment Start	Before Treatment Start	Before Treatment Start
YYYY = TRTY	(4.a)	(4.b)	(4.a)	(4.c)
	Uncertain	Before Treatment Start	Uncertain	After Treatment Start
YYYY > TRTY	(3.a) After Treatment Start	(3.b) After Treatment Start	(3.b) After Treatment Start	(3.b) After Treatment Start

- 1. If the CM start date year value is missing, the imputed CM start date is set to one day prior to treatment start date.
- 2. If the CM start date year value is less than the treatment start date year value, the CM started before treatment. Therefore:
 - a. If the CM month is missing, the imputed CM start date is set to the mid-year point (01JulYYYY).
 - b. Else if the CM month is not missing, the imputed CM start date is set to the midmonth point (15MONYYYY).
- 3. If the CM start date year value is greater than the treatment start date year value, the CM started after treatment. Therefore:
 - a. If the CM month is missing, the imputed CM start date is set to the year start point (01JanYYYY).
 - b. Else if the CM month is not missing, the imputed CM start date is set to the month start point (01MONYYYY).
- 4. If the CM start date year value is equal to the treatment start date year value:
 - a. And the CM month is missing or the CM month is equal to the treatment start date month, then the imputed CM start date is set to one day prior treatment start date.
 - b. Else if the CM month is less than the treatment start date month, the imputed CM start date is set to the mid-month point (15MONYYYY).

c. Else if the CM month is greater than the treatment start date month, the imputed CM

start date is set to the month start point (01MONYYYY).

If complete (imputed) CM end date is available and the imputed CM start date is greater than the (imputed) CM end date, then imputed CM start date should be set to the (imputed) CM end date.

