2.4.2 Prior, concomitant and post therapies

Prior medications and significant non-drug therapies are defined as any medication or significant non-drug therapy within 30 days prior to Visit Day1 with its start date prior to the date of Visit Day1. Concomitant medications and significant non-drug therapies are defined as any medication or significant non-drug therapy with its end date later than or equal to the date of the Visit Day1 and start date prior to or equal to the end date of the treatment period.

Prior and concomitant medications and significant non-drug therapies will be summarized by anatomical therapeutic classification (ATC), preferred term.

Concomitant heart failure medications (Angiotensin converting enzyme inhibitor (ACEI), Angiotensin receptor blocker (ARB), Beta-blockers, mineralcorticoid receptor antagonists (MRAs), diuretics (excluding MRAs), Cardiac glycocytes (Digoxin/digitalis glycoside), and sodium-glucose co-transporter2 inhibitors (SGLT2i)) will be summarized by medication category and preferred term.

In addition, the prior or concomitant medications and other non-drug therapies will be listed as follows:

← Medications

- Subject ID
- Date of Study Treatment start
- Start date (Treatment day)

Displays the start date entered on CRF or imputed and corresponding Treatment day (the number of days from the date of treatment start).

• End date (Treatment day)

Displays the end date entered on CRF or imputed and corresponding Treatment day (the number of days from the date of treatment start).

• On going

If the check box of 'On going' on CRF (the medication is ongoing at the end of the study), provide 'Yes'.

- Primary indication
- ATC
- Preferred term
- Reported medication name
- Dose
- Dose unit
- Frequency
- Route

≺ Non-drug therapies

- Subject ID
- Date of Study Treatment start
- Start date (Treatment day)

Displays the start date entered on CRF or imputed and corresponding Treatment day (the number of days from the date of treatment start).

• End date (Treatment day)

Displays the end date entered on CRF or imputed and corresponding Treatment day (the number of days from the date of treatment start).

• Primary Indication

• Procedure name

The SAF will be used for the above analyses.

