2.5.4 Handling of missing values not related to intercurrent event

The missing value for laboratory assessments, vital signs, height, weight, and other assessments will be not imputed.

The missing or partially missing start/end date for AEs, prior/concomitant therapies, and study drug will be imputed using the Novartis ADaM Governance Board (AGB) global standard approach. Details are provided in Section 5.1.

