5.1 Imputation rules

The missing or partially missing start/end date for AEs and prior/concomitant therapies will be imputed using the Novartis AGB global standard approach.

If the visit date is missing, the scheduled date (per protocol) of the visit will be used.

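### SAP 5.1.3 both forbids and prescribes imputing missing medication start dates, and its treatment-start anchor can strip prior status from an undated drug when study drug starts after Visit Day1

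*SAP*

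**What the plan says.** **Whether to impute.** The note in SAP 5.1.3 reads "Please note that missing start dates will not be imputed". Rule 1 in the same section reads "If the CM start date year value is missing, the imputed CM start date is set to one day prior to treatment start date". SAP 5.1 states: "The missing or partially missing start/end date for AEs and prior/concomitant therapies will be imputed using the Novartis AGB global standard approach". SAP 2.5.4 says the same and adds study drug: "The missing or partially missing start/end date for AEs, prior/concomitant therapies, and study drug will be imputed". Protocol 9.3.4 also announces imputation and leaves the rules to the SAP.

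**Which date to count from.** Rule 4a of SAP 5.1.3 covers a start in the same year as treatment start with the month missing or equal to the treatment-start month: "then the imputed CM start date is set to one day prior treatment start date". SAP 5.1.3.1 applies these rules to prior therapies too. SAP 2.4.2 classifies by another date. Prior therapy is therapy "within 30 days prior to Visit Day1 with its start date prior to the date of Visit Day1". Concomitant therapy needs an "end date later than or equal to the date of the Visit Day1 and start date prior to or equal to the" close of the treatment period.

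**Whether the two dates can differ.** Treatment normally starts at Visit Day1 (Protocol 1.3 and 8). Protocol 5.3 and footnote 1 of Table 1-2 allow enrolment without starting that day, provided treatment begins within 3 months of Visit Day1.

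**The concern.** There are two separate defects. First, a programmer who follows the note and one who follows rule 1 build different datasets from the same record. Second, even with rule 1 followed, imputation and classification use different reference dates. The rule's evident purpose is to place an undated drug just before the starting point, so that it counts as pre-existing. It does this relative to treatment start, but prior status is then judged relative to Visit Day1. For a late starter the imputed date falls on the wrong side of that line.

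What is at stake is the accuracy of the prior-therapy summary, and whether two people would produce the same table from the SAP. Long-standing background therapy is a plausible place for unknown start years, but that is my assumption; the documents give no rate.

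**Working it through.** **Are the note and rule 1 compatible?** One could try to limit the note to fully missing dates and rule 1 to partial ones. The SAP 5.1.3 matrix rules this out: the cell with both year and month missing points to rule 1, which supplies a date. The same note also stands in the adverse-event section, where it fits, because there "if the AE year value is missing, the imputed AE start date is set to NULL". It looks carried over into a section whose rule does the opposite.

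**What rule 1 does to classification.** Let D be Visit Day1, d the delay in days to first dose, and T = D + d.
- Imputed start (rule 1) = T − 1 = D + d − 1. If this is later than the end date, SAP 5.1.3 sets it back to the end date.
- Prior requires start < D, with use in the 30 days before D.
- Concomitant requires end ≥ D and start ≤ end of the treatment period.

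For a drug with unknown start year that is ongoing or has no end date (end imputed to treatment end + 1):

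| d (days) | Imputed start | Prior | Concomitant |
|---|---|---|---|
| 0 | D − 1 | yes | yes |
| 1 | D | no | yes |
| 2 | D + 1 | no | yes |
| 30 | D + 29 | no | yes |
| 60 | D + 59 | no | yes |
| 90 | D + 89 | no | yes |

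Two other end dates were checked over the same delays. A drug that ended at D + 20 behaves as in the table, except that from d = 30 its start is set back to D + 20; it is still concomitant and not prior. A drug that ended at D − 5 has its start set back to D − 5, so it is prior at every delay. Under rule 1 no record tested leaves both categories.

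**If the note were programmed instead.** The start stays empty. Both definitions in SAP 2.4.2 compare a start date, so read strictly the record meets neither.

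**Partial dates.** Assume Visit Day1 is 10 January 2024 and first dose 10 March 2024, so d = 21 + 29 + 10 = 60.
- Year 2024 only: rule 4a gives 9 March, which is D + 59, not prior. The drug may have begun on 1 to 9 January.
- January 2024, day missing: rule 4b gives 15 January, which is D + 5, not prior, with the same uncertainty.
- With Visit Day1 as reference date, both fall under rule 4a and become 9 January (D − 1), prior. February 2024 becomes 1 February and March 2024 becomes 1 March under rule 4c; both stay not prior, as they should.

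Rule 4b is therefore also affected, so changing rules 1 and 4a alone would not be enough.

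**After the change.** Rule 1 gives D − 1 at every d, so an ongoing undated drug is both prior and concomitant at all delays from 0 to 90 days. At present this holds only at d = 0.

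**The case against.** The case for leaving the text alone is strong on reach. The intent to impute is clear from SAP 2.5.4, SAP 5.1, Protocol 9.3.4 and the matrix, so the note is unlikely to be followed. The two dates coincide by default. The mismatch needs a late starter who also has an undated or partly dated drug, among at most 8 participants, and Protocol 10.1.5.2 provides for queries on missing values before lock. All of this stands and keeps the point minor.

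Three stronger readings are tempting, and the documents do not support them:
- *Long-standing drugs vanish from the tables.* This needs the note to override rule 1.
- *The heart-failure medication table is distorted.* SAP 2.4.2 builds that table from concomitant therapy, and under rule 1 a drug still in use at or after Visit Day1 remains concomitant, so its count does not move.
- *The listing shows the drug as newly started on study.* The medication listing shows treatment day, and (T − 1) − T + 1 = 0, which is the day before treatment day 1.

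One could also argue that Visit Day1 moves with treatment, since footnote 1 of Table 1-2 defers the Visit Day1 assessments to the visit when treatment starts. But the same footnote counts the 3 months from Visit Day1. SAP 2.1.1 fixes Visit Day1 to the Visit 599 date and sets baseline there whether or not drug is given that day, and the treatment-emergent definition in SAP 2.7.1 provides separately for a later start. The SAP treats the two dates as distinct.

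**Conclusion.** The point holds as a minor one. SAP 5.1.3 contradicts itself on whether missing start dates are imputed. With rule 1 applied, a late starter's drug that has an unknown start year, really began before Visit Day1 and is still in use loses prior status at any delay of 1 day or more. Partial dates can be affected in the same way.

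The size is one participant in a prior-therapy row per affected drug: 1/8 = 12.5 percentage points with 8 in the Safety Set, and more with fewer. Participants who start on Visit Day1 are unaffected, as are the concomitant and heart-failure tables under rule 1. So is the primary adverse-event endpoint, which uses no medication dates. Loss from both categories follows only if the note is programmed in place of rule 1.

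This rests on Visit Day1 keeping the Visit 599 date for late starters, and on at least one late starter having an unknown or partial start date. The documents do not say how often that occurs.

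**What to change.** Delete the no-imputation note from SAP 5.1.3. Use Visit Day1 in place of treatment start as the reference date for the whole medication start-date matrix, rules 1 to 4, with rules 1 and 4a imputing to Visit Day1 minus one day. Imputation and the SAP 2.4.2 classification then use the same date, and nothing changes for participants who start on Visit Day1.

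The cost is a few lines of SAP text and one changed reference date in a program. The downside is a study-specific departure from the sponsor's standard imputation approach, which the SAP should state.
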